2.5 Study Rationale

There remains a significant unmet medical need for new therapeutics for the treatment of SLE and LN. Bortezomib, a dual proteasome inhibitor, has shown promising clinical activity in patients with refractory SLE and LN, including patients who had failed to respond to standard immunosuppressive therapies, but systemic toxicities prevent long-term use in this patient population.

KZR-616 represents a new agent that can be administered as a single agent or, based on animal studies, in combination with background therapy and that may prove beneficial for patients with SLE and LN. We hypothesize that KZR-616 will rapidly induce clinically meaningful improvements in several markers for disease, including a reduction in proteinuria, at well tolerated doses.

Based upon the safety and efficacy in the Phase 2 portion of this study, it is anticipated that pivotal studies in LN will be initiated.

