2.5.3 Design Rationale

The Phase 1b portion of this trial is designed to evaluate the safety and tolerability of escalating doses of KZR-616 when administered in addition to standard-of-care therapy for 13 weeks in patients with SLE. The Phase 2 portion of this trial is designed to evaluate the renal response, safety and tolerability of KZR-616 when administered for 24 weeks in addition to standard therapy in patients with active proliferative LN.

In the Phase 1b portion, at least 6 patients per dose level will be enrolled to receive SC injections of KZR-616. Patients eligible for this part of the study must demonstrate adequate SLE disease activity at screening, be serologically positive, and may currently be on at least one SLE therapy, including oral corticosteroid, immunosuppressant (MMF, AZA, MTX, or leflunomide), and/or antimalarial agents, with stable dosage regimen. As these patients continue to have active SLE disease despite standard of care therapy, they are in need of an effective new treatment. As this is the first multiple dose study of KZR-616 in SLE patients, dose administration and step-wise evaluation is carefully outlined, including a sentinel patient in each dose cohort. Decisions to escalate, expand, or decrease dose level or frequency following the first 4 weeks of treatment for at least 4 evaluable patients in a cohort will depend on review by a Data Monitoring Committee (DMC).

In the Phase 1b portion of the study, a 4-week period of dose-limiting toxicity (DLT) evaluation for at least 4 evaluable patients in each cohort is proposed. Based on nonclinical toxicity studies, tolerability after 4 weeks of treatment is predictive of safety through 13 weeks of treatment. In addition, exposure data in healthy subjects show that KZR-616 is rapidly cleared and has no accumulation. Weekly administration of KZR-616 could be interpreted as serial episodic dosing, with potential AEs and DLTs likely to occur upon initial exposure and with a reduced risk with repeat dosing based on the results of KZR-616-001. These safety data will support the use of the RP2D of KZR-616 in patients with active proliferative LN for which there is a potential to increase the depth or frequency of response to background standard therapy. In addition, these data will be used to inform the design of future studies in non-renal SLE.

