In the Phase 2 portion of the study, a total of 20 patients with active proliferative Class III or IV LN (with or without Class V disease) will be enrolled to receive KZR-616 for a total of 24 weeks. Safety will be assessed throughout the 24 weeks of dose administration and the follow-up which will continue for 12 weeks post last dose. As this will be the first study of KZR-616 in patients with active proliferative LN, the data obtained are anticipated to be sufficient to enable design of future development studies for KZR-616.

Proof of activity is based on multiple disease response assessments in LN and SLE including evaluation for improvements in kidney function (changes in proteinuria and estimated glomerular filtration rate [eGFR]), changes in lupus disease assessments (Systemic Lupus Erythematosus Disease Activity Index 2000 [SLEDAI-2K] and, for the Phase 1b only, the British Isles Lupus Assessment Group [BILAG]), changes in serum biomarkers of disease (ANA, anti-dsDNA, anti-Smith, anti-ribonucleoprotein [anti-RNP], anti-Ro/La [anti-SSA/SSB], C3/C4, and 50% hemolytic complement [CH50]), and changes in daily corticosteroid use.

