11.2 Statistical Methods

11.2.1 Methods of Analysis

Verbatim AE terms will be coded using the Medical Dictionary for Regulatory Activities (MedDRA). The number and percentage of patients who experience AEs and SAEs will be summarized by dose/treatment group and overall.

Laboratory, vital sign, ECG, and efficacy data will be summarized descriptively (mean, median, standard deviation [SD], and minimum and maximum values) by dose/treatment group and overall and will be summarized by protocol specified time point along with a summary of change from baseline at each protocol specified time point. Changes in physical examinations will be listed for each patient and described.

PK analyses will include determination of plasma levels of KZR-616 including C_{\max} , T_{\max} , and AUC.

All patients who receive any amount of study drug (Safety Population) will be included in the safety analyses. Descriptive statistics, including the numbers and percentages for categorical variables and the numbers, means, SDs, medians, minimums and maximums for continuous variables will be provided by dose/treatment group overall.

11.2.2 *Analysis Population*

Safety Population

All patients who receive any amount of study drug will be included in the safety analyses.

PK Analysis Population

All patients who receive the Day 1 dose of KZR-616 and who have at least one post-dose concentration of KZR-616 measured will be included in the PK analysis population. Any protocol deviations affecting PK analyses may result in exclusion from summaries for individual time point concentrations, complete profiles, and/or PK parameters. These exclusions will be reviewed before database lock and confirmed with the sponsor before the implementation.

Pharmacodynamics Analysis Population

All patients who receive any amount of study drug and who have any measured results for PD assessment will be included in the PD analysis population. Any protocol deviations affecting PD analyses may result in exclusion from summaries for individual time point concentrations and/or complete profiles. These exclusions will be reviewed before database lock and confirmed with the sponsor before the implementation.

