11.3 Assessments

11.3.1 *Criteria for Evaluation – Safety Analysis*

Safety and tolerability is the primary endpoint for Phase 1b and a secondary endpoint for Phase 2.

Safety for the study will be evaluated through monitoring and assessment of all AEs, physical examination findings, vital sign measurements (blood pressure, pulse, and body temperature), ECGs, and clinical laboratory test results (hematology, serum chemistry, urinalysis) including quantitative serum immunoglobulins.

Severity of AEs will be assessed using the NCI-CTCAE, Version 4.03.

All AEs occurring on or after treatment on Week 1, Day 1 through Week 25, Day 169 for Phase 1b and through Week 37, Day 253 for Phase 2 will be summarized by MedDRA system organ class, preferred term, grade, and investigator assessment of causality.

In addition, all SAEs, including deaths, will be listed separately and summarized. Extent of exposure to the study treatment will be summarized using descriptive statistics.

Full details of the analyses will be specified in the statistical analysis plan (SAP). With regard to inconsistencies, the SAP will take precedence over the protocol.

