11.3.5 Criteria for Evaluation – Efficacy Analyses

Phase 2:

Assessment of Primary and/or Secondary Endpoints

Please see [Section 11.1.2](#) for a listing of secondary endpoints for Phase 2.

Rate of renal response will be assessed at 24 weeks. Renal response will be classified as complete, partial [50% reduction in UPCR], or no renal response. Summary statistics (e.g., total number of patients with observed data, mean, median, SD, min, max for continuous endpoints; for binary endpoints: total number of patients observed, number of patients with the event of interest, percent) will be provided by dose in Phase 1b and for all patients combined in Phase 2. The primary efficacy endpoint in Phase 2 is percent of patients with 50% reduction in UPCR after 24 weeks of treatment when compared to baseline. The null hypothesis is that the percentage is $\leq 20\%$; the alternative hypothesis is that the percentage is $> 20\%$. The test of hypotheses will be carried out with an exact binomial test. The KZR-616-002 Statistical Analysis Plan contains details of the planned analysis.

Phase 1b and Phase 2: Exploratory Endpoints:

The efficacy of KZR-616 on SLE will be assessed using changes from baseline in study administered questionnaires/disease assessment tools and changes from baseline in laboratory measures.

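### Does testing the Phase 2 response rate against 20% in one uncontrolled arm of 20, with no interval listed, need a change to Section 11.3.5?

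*Combined protocol and SAP*

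**What the plan says.** Section 11.3.5 sets a null of at most 20% and an alternative above 20% for the Phase 2 primary endpoint, and states that "The test of hypotheses will be carried out with an exact binomial test". Its summary statistics are introduced as examples and include, "for binary endpoints: total number of patients observed, number of patients with the event of interest, percent". Section 11.2.1 adds that "efficacy data will be summarized descriptively". Neither place mentions a confidence interval, and neither gives an alpha or a basis for the 20%.

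Section 4.1.2 describes Phase 2 as open-label at one dose level in 20 patients, all on standard therapy with at least one immunosuppressant. Section 11.4 says the study is not powered by hypothesis testing.

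On purpose, Section 2.5 says "We hypothesize that KZR-616 will rapidly induce clinically meaningful improvements in several markers for disease, including a reduction in proteinuria". Section 2.5.3 says "the data obtained are anticipated to be sufficient to enable design of future development studies for KZR-616" and also "Proof of activity is based on multiple disease response assessments in LN and SLE".

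Section 11.3.5 refers the reader to the SAP for the planned analysis, and Section 11.3.1 closes with "With regard to inconsistencies, the SAP will take precedence over the protocol". The combined document contains no separate SAP text.

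**The concern.** The drug is given on top of background therapy, so the clinically useful question is whether it adds anything. A test against a fixed 20% in one arm cannot answer that unless 20% is a sound ceiling for response on background therapy alone, and the document does not say where the figure comes from.

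The only background rates supplied are in Section 2.2: about 50% with improved proteinuria and about 25% with complete renal response after 1 year on guideline regimens. Both are above 20%. Background response may also still be developing during the study. Section 5.2.3 asks for only 8 weeks of stable immunosuppressant, so a patient can be assessed at about week 8 + 24 = 32 of a regimen. Section 7.2.2 has patients who finish a EuroLupus cyclophosphamide course start another immunosuppressive regimen on study.

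This is the only formal efficacy test in the text, and Section 2.5 anticipates pivotal nephritis studies on the strength of Phase 2. A p-value just under the threshold, reported with a count and a percentage but no interval or caveat, could be taken as an effect over background when it is only weak evidence of one.

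**Working it through.** **Inputs.** n = 20 (Section 5.1); null rate 0.20, upper-tailed exact binomial test (Section 11.3.5). Alpha is not in the text, so one-sided 0.05 and 0.025 are both assumed. There is no stated power or alternative rate to reproduce, in keeping with Section 11.4.

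**Rejection boundary.** With X the number of responders, p = P(X ≥ r | n = 20, 0.20) = Σ C(20,k) 0.2^k 0.8^(20−k) for k = r to 20.

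- r = 7: 0.0867, not rejected at either level
- r = 8: 0.0321, rejected at 0.05 only
- r = 9: 0.0100, rejected at both

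The boundary is therefore 8/20 (40%) at 0.05 and 9/20 (45%) at 0.025. It depends on how many patients are observed. Replacement before Week 14 (Section 5.1) and no imputation (Section 11.3.6) can move n. At one-sided 0.05 the boundary is 7 for n = 15 to 17, 8 for n = 18 to 21, and 9 for n = 22.

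**Exact (Clopper-Pearson) interval.** The lower limit is the a/2 quantile of Beta(r, 21 − r) and the upper limit the 1 − a/2 quantile of Beta(r + 1, 20 − r), with a = 0.10 (90%) or 0.05 (95%).

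| Responders | 90% interval | 95% interval |
|---|---|---|
| 8/20 | 21.7% to 60.6% | 19.1% to 63.9% |
| 9/20 | 25.9% to 65.3% | 23.1% to 68.5% |
| 10/20 | 30.2% to 69.8% | 27.2% to 72.8% |
| 12/20 | 39.4% to 78.3% | 36.1% to 80.9% |
| 15/20 | 54.4% to 89.6% | 50.9% to 91.3% |

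The 90% lower limit exceeds 20% exactly when the test rejects at one-sided 0.05, and the 95% lower limit exactly when it rejects at 0.025. The levels need to match: 8/20 rejects at one-sided 0.05 although its 95% interval includes 20%.

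**If KZR-616 added nothing.** The chance of reaching the boundary at an assumed background rate is P(X ≥ r | n = 20, that rate):

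| Background rate | P(X ≥ 8) | P(X ≥ 9) |
|---|---|---|
| 15% | 0.006 | 0.001 |
| 25% | 0.10 | 0.04 |
| 30% | 0.23 | 0.11 |
| 35% | 0.40 | 0.24 |
| 40% | 0.58 | 0.40 |
| 50% | 0.87 | 0.75 |

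These rates are illustrative. The Section 2.2 figures differ from this endpoint in definition, time point and population, so none of the rows is established for this trial. Larger counts are harder to put down to background: 10/20 gives p = 0.048 against 30%, and 15/20 gives p = 0.021 against 50%.

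**What the numbers mean.** A trial with no background-only arm rules out no background rate. At 9/20, a background rate of 10% remains possible, and the count would then point to a drug effect. The lower limit says only that a background rate at or below it would not, by itself, readily explain the count.

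**The case for a change.** The best case for a change is that rewording costs almost nothing and is best settled before results are known. It would add an exact interval at the level matching alpha, a sentence that rejection does not by itself show an effect over background, and either a source for 20% or a label of descriptive, which would also ease the tension with Section 11.4. Several facts behind this stand. Alpha, the basis for 20% and the interval are absent from the text, and a boundary result is weak evidence of an add-on effect.

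The rest of the case is weaker. The list of binary summaries is given as examples, so the absence of an interval from it does not mean that none will be reported. The remark in Section 2.5.3 that "there is a potential to increase the depth or frequency of response to background standard therapy" closes a paragraph on Phase 1b dose-limiting toxicity and on how those safety data support the Phase 2 dose. It does not describe what the 20% test is meant to prove. The Phase 2 primary objective in Section 3.2 is only to assess how many patients reach a 50% reduction.

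Nor is 20% shown to be too low. Sections 5.2.3 and 8.2.6.5 require UPCR of at least 1.0 on two 24-hour collections despite stable treatment, which could well put the background rate below the Section 2.2 figures. The feared misreading is a matter of later reporting, and no passage invites it.

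**Conclusion.** No change is needed. Followed as written, the plan leads to a sound conclusion for the hypothesis it states: the response rate on KZR-616 plus background therapy does, or does not, exceed 20%. At the boundary that conclusion is modest, with a matched exact lower limit of 21.7% for 8/20 (one-sided 0.05) or 23.1% for 9/20 (one-sided 0.025). No go/no-go rule uses the p-value, and Section 2.5.3 rests proof of activity on several assessments, though all come from the same arm.

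The interval is a gap an analyst fills routinely from the count, at the level matching the alpha used. Alpha and the basis for 20% belong to the detail that Section 11.3.5 assigns to the SAP. The lack of a control is evident from the design, and readers should interpret any rejection in that light.

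This rests on 20 observed patients, on an assumed one-sided alpha of 0.05 or 0.025, and on no use of the test as evidence of an effect over background. The true background rate for this endpoint is unknown from the document.

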11.3.6 Handling of Missing Data

All withdrawals will be included in all analyses up to the time of withdrawal. Patients who are withdrawn prematurely from investigational product and/or the study will be included in all analyses regardless of the duration of treatment. There will be no imputation for missing data, unless otherwise specified.

11.4 Determination of Sample Size

The study is not powered using statistical hypothesis testing.

11.5 Interim Analysis

Review of safety data will be carried out after each cohort in Phase 1b as explained above. There is no formal statistical interim analysis planned.

12 ETHICAL AND ADMINISTRATIVE CONSIDERATIONS

12.1 Compliance Statement

The investigator(s) and all parties involved in this study should conduct the study in adherence to the ethical principles based on the Declaration of Helsinki, International Council for Harmonisation (ICH) guidelines for current Good Clinical Practice (cGCP), and the applicable national and local laws and regulatory requirements.

Relevant study documentation will be submitted to the regulatory authorities of the participating countries, according to local/national requirements, for review and approval before the beginning of the study. On completion of the study, the regulatory authorities will be notified that the study has ended.

12.2 Institutional Review Board or Independent Ethics Committee

Before initiation of the study at each study center, the protocol, the ICF, other written material given to the patients, and any other relevant study documentation will be submitted to the appropriate IEC/IRB. Written approval of the study and all relevant study information must be obtained before the study center can be initiated or the study drug is released to the investigator. Any necessary extensions or renewals of IEC/IRB approval must be obtained for changes to the study (i.e., amendments to the protocol, the ICF, or other study documentation). The written approval of the IEC/IRB together with the approved ICF must be filed in the study files.

The investigator will report promptly to the IEC/IRB any new information that may adversely affect the safety of the patients or the conduct of the study. The investigator will submit written summaries of the study status to the IEC/IRB as required. On completion of the study, the IEC/IRB will be notified that the study has ended.

12.3 Informed Consent and Human Patient Protection

The process of obtaining informed consent must be in accordance with applicable regulatory requirement(s) and must adhere to current Good Clinical Practice (GCP).

Patients will provide written informed consent before any study-related procedures are performed.

The investigator is responsible for ensuring that no patient undergoes any study-related examination or activity before that patient has given written informed consent to participate in the study.

The investigator or designated personnel will inform the patient of the objectives, methods, anticipated benefits, and potential risks and inconveniences of the study. The patient should be given every opportunity to ask for clarification of any points s/he does not understand and, if necessary, ask for more information. At the end of the interview, the patient will be given ample time to consider the study. Patients will be required to sign and date the ICF. After signatures are obtained, the ICF will be kept and archived by the investigator in the

investigator's study file. A signed and dated copy of the patient ICF will be provided to the patient or their authorized representative.

It should be emphasized that the patient may refuse to enter the study or to withdraw from the study at any time, without consequences for their further care or penalty or loss of benefits to which the patient is otherwise entitled. Patients who refuse to give or who withdraw written informed consent should not be included or continue in the study.

If new information becomes available that may be relevant to the patient's willingness to continue participation in the study, a new ICF will be approved by the IEC(s)/IRB(s) (and regulatory authorities, if required). The study patients will be informed about this new information and re-consent will be obtained.

12.4 Direct Access to Source Data, Source Documents, and Study Records

Kezar or its representatives may periodically check a sample of the patient data recorded against source documents at the study site. The study may be audited by Kezar and/or regulatory agencies at any time. Investigators will be given notice before an audit occurs.

The investigator will keep records of all original source data. This might include laboratory tests, medical records, and clinical notes. If requested, the investigator will provide the sponsor, applicable regulatory agencies, and applicable review boards with direct access to the original source documents.

12.5 Data Collection and Handling

An EDC system will be used in this study. The site must define and retain all source records and must maintain a record of any data where source data are directly entered into the data capture system.

Data systems used for the study will have controls and requirements in accordance with local data protection law.

The purpose and use of patient personal information collected will be provided in a written document to the patient by the sponsor.

12.6 Confidentiality

Monitors, auditors, and other authorized agents of the sponsor and/or its designee, the IEC(s)/IRB(s) approving this research, and the FDA, as well as that of any other applicable agency(ies), will be granted direct access to the study patients' original medical records for verification of clinical study procedures and/or data, without violating the confidentiality of the patients to the extent permitted by the law and regulations. In any presentations of the results of this study or in publications, the patients' identity will remain confidential.

All personal data collected and processed for the purposes of this study should be managed by the investigator and his/her staff with adequate precautions to ensure confidentiality of

those data, and in accordance with the Health Insurance Portability and Accountability Act, applicable to national and/or local laws and regulations on personal data protection.

12.7 Financing and Insurance

Financing and insurance of this study will be outlined in a separate agreement between the CRO and the sponsor.

12.8 Audit and Inspection

Study centers and study documentation may be subject to Quality Assurance audit during the course of the study by the sponsor or its nominated representative. In addition, inspections may be conducted by regulatory authorities at their discretion.

12.9 Monitoring

Data for each patient will be recorded on an eCRF. Data collection must be completed for each patient who signs an ICF and is administered study drug.

In accordance with cGCP and ICH guidelines, the study monitor will carry out source document verification at regular intervals to ensure that the data collected in the eCRF are accurate and reliable.

The investigator must permit the monitor, the IEC/IRB, the sponsor's internal auditors, and representatives from regulatory authorities' direct access to all study-related documents and pertinent hospital or medical records for confirmation of data contained within the eCRFs.

